## **1. SYNOPSIS**

Trial Title	Phase I/II Study to Evaluate the Safety, Efficacy, and Novel PET/CT Imaging Biomarkers of CB-839 in Combination with Panitumumab and Irinotecan in Patients with Metastatic and Refractory RAS Wildtype Colorectal Cancer.
Phase I Trial Design	This is a three-agent, open-label, non-randomized, Phase I dose escalation study of combinatorial oral CB-839 plus infusional panitumumab and irinotecan in patients with metastatic RAS wildtype colorectal cancer. The phase I portion was designed in order to collect toxicity data of the triplet combination, as this treatment regimen could go forward in clinical development.
Phase II Trial Design	This is a two-agent, open-label, non-randomized, Phase II dose expansion study of combinatorial oral CB-839 plus infusional panitumumab in patients with metastatic and refractory RAS wildtype colorectal cancer. The phase II portion is a hypothesis driven study to investigate the efficacy of adding a glutaminase 1 inhibitor to single agent anti-EGFR monoclonal antibody therapy.
Trial Sites	Vanderbilt University Medical Center
Study Drug and Mechanism	CB-839 is an oral small molecule inhibitor of glutaminase 1 under investigation for the treatment of various solid and hematologic malignancies, where alterations in glutamine metabolism may play a role in cancer cell growth and survival. Regulatory approval has not been sought and CB-839 is not approved or marketed in any country. Calithera will provide CB-839 to the site.
Standard of Care Drugs and Mechanisms	Panitumumab (VECTIBIX) is a recombinant, human IgG2 kappa monoclonal antibody that binds to the human epidermal growth factor receptor (EGFR). Binding of panitumumab to EGFR thus inhibits ligand-induced tyrosine phosphorylation of EGFR. Panitumumab is FDA-approved for the treatment of wild-type KRAS metastatic colorectal cancer (mCRC): In combination with FOLFOX for first-line treatment; and as monotherapy following disease progression after prior treatment with fluoropyrimidine, oxaliplatin, and irinotecan-containing chemotherapy. The site will obtain panitumumab from commercial supply.  Irinotecan (CAMPTOSAR) is a topoisomerase inhibitor. Irinotecan is a derivative of camptothecin. Irinotecan and its active metabolite SN-38 bind to the topoisomerase I-DNA complex, thus inhibiting re-ligation of single-strand breaks induced by topoisomerase intended to relieve torsional strain during DNA replication. Irinotecan is FDA approved, in combination with 5-fluorouracil and leucovorin, for patients with metastatic carcinoma of the colon or rectum; and for patients with metastatic carcinoma of the colon or rectum whose disease has recurred or progressed following initial fluorouracil-based therapy. The site will obtain irinotecan as standard of care from commercial supply.

Treatment Schedule	
Treatment will consist of Cycles lasting 4 weeks (28 days) each.
 
All patients (both phases) are scheduled to receive oral CB-839 twice daily (BID) on a continuous dosing schedule.
 
All patients (both phases) are scheduled to receive panitumumab as a 60 minute (if dose <math>\leq</math> 1000 mg) or 90 minute (if dose <math>></math> 1000 mg) intravenous infusion on Day 1 and Day 15 of each 28 day cycle.
 
All patients in phase I only are scheduled to receive irinotecan as a 90-minute intravenous infusion on Day 1 and Day 15 of each 28 day cycle.
 
On days when both panitumumab and irinotecan drugs are administered (i.e. scheduled for Days 1 and 15 of each cycle), the panitumumab infusion will be completed BEFORE initiation of the irinotecan infusion.

Objectives and Outcome Measures	
Objectives:
 
Primary Objective of Phase I:
 
 
Determine the safety and tolerability of CB-839 in combination with panitumumab and irinotecan.
 
 
Exploratory Objective of Phase I (Optional Imaging Sub-study):
 
 
Correlate radiological features of pre- and post-treatment <math>^{11}\text{C}</math>-Glutamine PET/CT and <math>^{18}\text{F}</math>-FSPG PET/CT with clinical outcome.
 
 
Primary Objective of Phase II:
 
 
Determine the efficacy of CB-839 in combination with panitumumab as measured by the response rate (RR).
 
 
Secondary Objectives of Phase II:
 
 
Determine the disease control rate (DCR), progression-free survival (PFS), and overall survival (OS).
 
Perform the following correlative studies (in the phase 2 component): 
 
Correlate radiological features of pre- and post-treatment <math>^{18}\text{F}</math>-FSPG PET/CT with clinical outcome and biological correlates (tissue gene signature, exosomes).
 
Collect blood samples during each radiotracer injection to assess pharmacokinetics.
 
Collect pre-treatment biopsy tissue and prospectively correlate clinical outcome with a glutamine metabolism gene signature.
 
Quantify exosomal content in the plasma.
 
 
 
 
Exploratory Objective of Phase II:
 
 
Development of patient-derived organoids from pre-treatment tissue biopsy
 
 
Endpoints:
 
Primary Endpoint of Phase I:
 
 
Maximum Tolerated Dose (MTD) and recommended phase 2 dose (RP2D) of CB-839 in combination with standard doses of panitumumab and irinotecan.
 
 
Exploratory Endpoint for Phase I (Optional Imaging Sub-study):
 
 
Maximum Standardized Uptake Value (SUVmax) of <math>^{11}\text{C}</math>-Glutamine and <math>^{18}\text{F}</math>-FSPG uptake at pre-treatment and after one cycle of treatment.
 

	
Primary Endpoint of Phase II:
 
 
• Response Rate (RR) of CB-839 in combination with panitumumab.
 
 
Secondary Endpoints of Phase II:
 
 
• Disease control rate (DCR), Progression-free Survival (PFS), and Overall Survival (OS).
 
• Maximum Standardized Uptake Value (SUVmax) of F-FSPG uptake at pre-treatment and after one cycle of treatment.
 
• Glutamine metabolism gene signature using qRT-PCR analysis and RNA-Seq.
 
• Radiotracer pharmacokinetic modeling parameters
 
• Plasma exosomal content at pre-treatment, after one cycle of treatment, and at disease progression.
 
 
Exploratory Endpoint for Phase II:
 
 
• Development of patient-derived organoid model
 

Main Inclusion and Exclusion Criteria	
Main inclusion criteria:
 
 
• Histologically or cytologically-confirmed diagnosis of metastatic RAS wildtype colorectal cancer (CRC).
 
• ECOG performance status of 0 or 1.
 
• In Dose Escalation, patients must have had at least one prior line of chemotherapy for advanced disease or progressed within 6 months of adjuvant therapy (prior chemotherapy and/or anti-EGFR therapy is permitted).
 
• In Dose Expansion, patients must have received prior anti-EGFR therapy and achieved at least stable disease on at least one scan as their best response.
 
• In Dose Expansion, patients must be willing to undergo a pre-treatment biopsy, and four research PET imaging techniques (C-Glutamine and F-FSPG), two pre-treatment and two after one cycle of treatment.
 
• Adequate organ function including: 
 
— Absolute neutrophil count (ANC) <math>\geq 1,500/\mu\text{L}</math>
 
— Platelets <math>\geq 100,000/\mu\text{L}</math>
 
— Serum albumin <math>\geq 3.0 \text{ g/dL}</math>
 
— Serum creatinine <math>\leq 2 \text{ mg/dL}</math>, or calculated creatinine clearance <math>> 50 \text{ mL/min}</math> (per the Cockcroft-Gault formula)
 
— Total bilirubin <math>\leq 1.5</math> times upper limit of normal (ULN)
 
— Aspartate transaminase (AST) and Alanine Aminotransferase (ALT) <math>\leq 5.0 \times \text{ULN}</math>.
 
 
 
 
Main exclusion criteria:
 
 
• Within 28 days before first dose of protocol-indicated treatment: 
 
— Anti-cancer treatment including chemotherapy, radiation, hormonal therapy, targeted therapy, immunotherapy, or biological therapy.
 
— Major surgery requiring general anesthesia. (Note: within this time frame, placement of a central line or portacath is acceptable and does not exclude.)
 
— Receipt of an investigational agent.
 
 
 
• Within 14 days before first dose of protocol-indicated treatment: 
 
— Active uncontrolled infection. Patients with infection under active treatment and controlled with antibiotics initiated at least 14 days prior to initiation of protocol-indicated treatment are not excluded (e.g. urinary tract infection controlled with antibiotics).
 
 
 


	
 
• For Dose Escalation only: Known Grade 4 toxicity probably or definitely attributed to past irinotecan treatment.
 
• Active inflammatory bowel disease, other bowel disease causing chronic diarrhea (defined as > 4 loose stools per day), or bowel obstruction.
 
• History of interstitial pneumonitis or pulmonary fibrosis, or evidence of interstitial pneumonitis or pulmonary fibrosis on baseline chest CT scan.
 
• Unable to receive oral medication.
 
• CNS metastasis, unless asymptomatic or previously treated and stable; and no evidence of CNS progression for at least 30 days prior to initiating protocol-indicated treatment. Anticonvulsant and/or corticosteroid therapy will be allowed if patient is on a stable or decreasing dose of such treatment for at least 30 days prior to initiating protocol-indicated treatment.
 
																
Overall Trial Design	
Phase I: Dose-Escalation:      Bayesian continual reassessment method with the following intended dose levels:
 
  
 Dose Level	CB-839 Oral continuous BID	Panitumumab I.V. Days 1 and 15	Irinotecan I.V. Days 1 and 15	
   
 -1	400 mg	6 mg/kg	180 mg/m^2	
 
 1	600 mg	6 mg/kg	180 mg/m^2	
 
 2	800 mg	6 mg/kg	180 mg/m^2	
  
 
1 cycle = 28 days
 
Patients will be treated in cohorts of 3. All toxicity outcomes must be observed before calculating the recommended dose level for the next cohort. Dose levels may not be skipped. Up to 12 patients may be enrolled since there are 2 working dose levels and a -1 dose level to be evaluated and a minimum of 6 patients are required to establish the MTD.
 
Phase II:      Patients enrolled will be treated at the MTD (or recommended phase 2 dose [RP2D]) of CB-839 determined from phase I. Enrollment will use a Simon's optimal 2-stage design to monitor efficacy (best overall response rate). If zero responses are observed in the first 10 patients, we will stop accrual for lack of efficacy. Otherwise we will continue accrual up to 29. If 4 or more patients achieve a response among 29 treated, we reject the null hypothesis (<math>p < 0.05</math>) of low efficacy (<math>RR \leq 5\%</math>) and declare this regimen sufficiently active in this patient population to warrant further study in more definitive trials.
	Dose Level	CB-839 Oral continuous BID	Panitumumab I.V. Days 1 and 15	Irinotecan I.V. Days 1 and 15	-1	400 mg	6 mg/kg	180 mg/m 	1	600 mg	6 mg/kg	180 mg/m 	2	800 mg	6 mg/kg	180 mg/m 
Dose Level	CB-839 Oral continuous BID	Panitumumab I.V. Days 1 and 15	Irinotecan I.V. Days 1 and 15														
-1	400 mg	6 mg/kg	180 mg/m 														
1	600 mg	6 mg/kg	180 mg/m 														
2	800 mg	6 mg/kg	180 mg/m 														
Number of Patients	
Approximately 40 total patients: About 9-12 eligible patients are anticipated during phase I, and up to 29 patients in phase II.
																

Planned Enrollment Period	Overall enrollment is anticipated to last approximately 24 months.
Study Assessments	See the Schedule of Assessments in Section 6.

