### **4.1. Inclusion Criteria**

Patients must meet all of the following inclusion criteria to be eligible for enrollment into the study:

1. Signed and dated written informed consent.
2. Male or female  $\geq 18$  years of age.
3. Histologically or cytologically-confirmed diagnosis of metastatic *KRAS* wildtype colorectal cancer (CRC).
4. Eastern Cooperative Oncology Group (ECOG) performance status of 0 or 1.
5. In Dose Escalation, patients must have had at least one prior line of chemotherapy for advanced disease or progressed within 6 months of adjuvant therapy (prior chemotherapy and/or anti-EGFR therapy is permitted).

6. In Dose Expansion, patients must have received prior anti-EGFR therapy and achieved at least stable disease on at least one scan as their best response.
7. In Dose Expansion, patients must be willing to undergo a pre-treatment biopsy, and two research PET imaging techniques (F-FSPG), one at pre-treatment and one after one cycle of treatment.
8. In Dose Expansion, at least one measurable lesion as defined by RECIST 1.1 which can be followed by CT or MRI.
9. Adequate organ function including:
  - Absolute neutrophil count (ANC)  $\geq 1,500/\mu\text{L}$
  - Platelets  $\geq 100,000/\mu\text{L}$
  - Serum albumin  $\geq 3.0 \text{ g/dL}$
  - Serum creatinine  $\leq 2 \text{ mg/dL}$ , or calculated creatinine clearance  $> 50 \text{ mL/min}$  (per the Cockcroft-Gault formula)
  - Total bilirubin  $\leq 1.5$  times upper limit of normal (ULN)
  - Aspartate transaminase (AST) and Alanine Aminotransferase (ALT)  $\leq 5.0 \times \text{ULN}$ .
10. Women of childbearing potential (WOCBP) must have a negative serum pregnancy test within 14 days prior to receiving first dose of protocol-indicated treatment; and additionally agree to use at least 2 methods of acceptable contraception (Appendix 4) or abstain from heterosexual intercourse from the time of signing consent, and until 2 months after patient's last dose of protocol-indicated treatment.

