#### **4.5. Optional Imaging Sub-Study for Phase I (Maximum of 9 patients)**

Patients accrued to the Phase I Dose Escalation portion of this study may optionally participate in an imaging sub-study. Patients must sign the optional consent for participation in this sub-study and be willing to undergo four research PET imaging techniques (C-Glutamine and F-FSPG), two pre-treatment and two after one cycle of treatment. Please refer to Table 6.1 for details regarding the timing of relevant assessments.

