### **5. ENROLLMENT PROCEDURES**

#### **5.1. Guidelines for VICC**

The Vanderbilt-Ingram Cancer Center (VICC) Coordinating Center will coordinate enrollment in the study.

Prior to registration, a copy of the IRB approval at the site will be kept on file at the Vanderbilt-Ingram Cancer Center (VICC) Coordinating Center. Eligible participants will be entered on study centrally at the VICC Coordinating Center. All sites should email the Coordinating Center at [REDACTED] to verify slot availability prior to enrollment.

All patients **MUST** be registered with the Vanderbilt-Ingram Cancer Center (VICC) prior to the start of study procedures such as tissue acquisition. Registration can only be conducted during the business hours of 8AM – 5PM Central Time, Monday through Friday.

- 1) All sites must email the VICC CTSR Coordinating Center at [REDACTED] to notify of upcoming registration and ensure slot availability. The following information should be included in this email:

- Study number.
- Patient initials.
- Disease type.

- Anticipated consent date.
- Anticipated start date.

2) If a subject ID number is required prior to patient enrollment (i.e. at screening due to sample collection requirement), the site must submit the following documents with their email notification to the Coordinating Center:

- Copy of the patient's signed and dated Informed Consent including documentation of the consent process.
- HIPAA authorization form (if separate from the main consent form).
- VICC Patient Enrollment Form.

The Coordinating Center will then provide a subject ID number via email.

3) Email the following documents to the Coordinating Center for eligibility review and patient enrollment [REDACTED]

- Copy of the patient's signed and dated Informed Consent, including documentation of the consent process.
- HIPAA authorization form (if separate from the main consent form).
- VICC Patient Enrollment Form.
- Eligibility supporting documents such as pathology reports, laboratory tests, etc. or EMR access. Note: all source documents should be de-identified and screening/subject ID number added prior to sending.
- Tissue Block Registration Form
- Signed and completed Eligibility Checklist. **To be eligible for registration to the study, the participant must meet each inclusion and exclusion criterion listed in the eligibility checklist.**

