## 6. SCHEDULE OF ASSESSMENTS

### 6.1. Study Calendar

Protocol Activities 1 Cycle = 4 weeks (28 days)	Screening (Day -14 to Day -1)	CYCLE 1			CYCLES ≥ 2		Post-Treatment	
		Day 1	Day 15	Day 28 	Day 1 (± 1 day) 	Day 15 (± 1 day) 	EOT (≤ 14d after last treatment) 	Follow-Up (28d + 7d after last study dose) 
Assessments & Observations								
Consent, Baseline Characteristics & Eligibility 	X							
Physical and Skin Examination 	X	X 	X		X	X	X	X
ECOG Performance Status	X	X	X		X	X	X	X
Vital Signs	X	X	X		X	X	X	X
Height	X							
Weight 	X	X 	X		X	X	X	X
Review of Con Meds and Adverse Events 	X	X	X		X	X	X	X
Study Drug Compliance (Dosing Diary)			X	X	X		X	
DLT Evaluation (dose-escalation only) 		X	X	X	X			
Laboratory Assessments								
Hematology and Blood Chemistry 	X	X 	X		X	X	X	X
Urinalysis	X							
Pregnancy Test 	X	X		X			X	
Disease Assessments								
CT or MRI Scan 	X				X		X 	X 
 C-Glutamine PET/CT (Optional in Phase I only, not performed in Phase II) 	X 			X 				
 F-FSPG PET/CT (Optional in Phase I) 	X 			X 				
Survival Follow-Up								X 
Biospecimen Collections								
Research Tumor Biopsy (Phase II Only)	X							
Pharmacokinetic (PK) Blood (Optional in Phase I) 	X			X				
Pharmacodynamic (PD) Blood (Phase II Only) 		X		X			X	
Treatment								
CB-839 oral administration 		Continuous oral twice daily dosing 						
Panitumumab infusion 		X	X		X	X		
Irinotecan infusion (Phase I Only) 		X	X		X	X		

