### **7.12.1 C-Glutamine Radiochemistry**

[C]Carbon dioxide will be produced by bombardment of N2 gas in the presence of a small percentage of O2 with high energy protons to induce the N(p,a) C nuclear reaction. Following the irradiation, the target gas will be processed with a GE Procab module. Briefly, the [C]CO2 will be trapped on activated molecular sieves, then mixed with a nickel catalyst and reacted at 400°C in the presence of hydrogen gas to provide [C]CH4. [C]CH4 will then be reacted with ammonia over a platinum catalyst at 950°C. The [C]HCN produced will be transferred to an automated synthesis module and bubbled into a solution containing 18-crown- 6 (18-C-6) and CsHCO3 in N,N-dimethylformamide at room temperature. To this reaction mixture will then be added (2S)-2-[(tertbutoxycarbonyl)amino]-4-iodobutanoate, followed by heating at 90°C for a period 8 minutes. The reaction mixture will then be diluted with H2O and purified via solid-phase extraction (SPE). The radioactivity will then be eluted from the SPE cartridge into a second reactor using pure acetonitrile. The intermediate will then be azeotropically dried by iterative additions and evaporation of acetonitrile. Once completely dry, a solution of trifluoroacetic acid/sulfuric acid will then be added to the reactor, and the reaction mixture will be heated at 90°C for 5 min. Following dilution of the product with H2O, the mixture will then be loaded onto an Ag11-A8 resin packed column, drained, and then eluted with additional H2O to give the desired C-Glutamine.

Table 1: Number of subjects to be studied with each proposed radiotracer

Radiotracer	Total Number of patients to be studied
-------------	--

 F-FSPG PET/CT	29
 C-Glutamine PET/CT (optional for phase I)*	29
<small>*Note: An IND will be sought after 15 participants have been imaged with C-Glutamine</small>	

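### The synopsis and Section 4.1 set different PET conditions for Phase II entry, and the 11C-Glutamine patient counts do not fit the tracer's 9-patient cap

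*Combined protocol and SAP*

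**What the plan says.** **Entry criterion.** The synopsis, under main inclusion criteria, states: "In Dose Expansion, patients must be willing to undergo a pre-treatment biopsy, and four research PET imaging techniques". It names 11C-Glutamine and 18F-FSPG and times the scans as "two pre-treatment and two after one cycle of treatment". Section 4.1 item 7 reads: "In Dose Expansion, patients must be willing to undergo a pre-treatment biopsy, and two research PET imaging techniques". It names 18F-FSPG only, with one scan before treatment and one after cycle 1.

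**Schedule.** The Section 6.1 calendar labels the 11C-Glutamine row "Optional in Phase I only, not performed in Phase II".

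**Registration.** Section 5.1 says that "the participant must meet each inclusion and exclusion criterion listed in the eligibility checklist". The checklist itself is not part of the documents.

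**11C-Glutamine numbers.** Section 4.5 caps the optional Phase I imaging sub-study at 9 patients. Table 1 (Section 7.12.1) lists 29 patients for 18F-FSPG and 29 for 11C-Glutamine, with the footnote "An IND will be sought after 15 participants have been imaged with" 11C-Glutamine. Sections 2.6.2 and 7.12 expect enough data for an IND submission after roughly 15 patients. Section 2.6.2 also describes the imaging as first-in-human for this tracer.

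**The concern.** The same Phase II criterion stands in the current text in two versions that cannot both apply. Willingness to be imaged decides who may enter and what patients are asked to consent to, and one version includes a tracer not previously used in humans. If the checklist or consent form took its wording from the synopsis, patients who qualify under Section 4.1 could be refused, or could be asked to agree to scans that the schedule does not contain.

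The 11C-Glutamine counts add to the confusion. A reader who suspects that the synopsis line is wrong and turns to Table 1 finds 29 patients there, which appears to support it. The IND expectation and parts of Section 15 likewise assume more 11C-Glutamine data than this protocol can produce.

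**Working it through.** **1. The criterion, side by side**

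| Place | Phase II requirement | 11C-Glutamine in Phase II? |
|---|---|---|
| Synopsis, main inclusion criteria | 4 scans, two tracers | Yes |
| Section 4.1 item 7 | 2 scans, 18F-FSPG | No |
| Section 6.1 calendar and note 13 | 18F-FSPG required | No |
| Section 6.2 (screening) | 18F-FSPG; 11C-Glutamine for the Phase I sub-study only | No |
| Section 6.5 (Cycle 1, Day 28) | 18F-FSPG | Not listed |
| Sections 7.11, 7.12, 12.4 | 18F-FSPG required; 11C-Glutamine optional in Phase I | No |
| Section 15 | Two 18F-FSPG sessions | No session stated |

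The synopsis's own Phase II objectives and endpoints also name only 18F-FSPG. The four-scan, two-tracer wording matches the optional Phase I sub-study in Section 4.5.

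**2. Scans implied by each version** (tracers × time points)

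- Synopsis: 2 × 2 = 4 per patient, of which 1 × 2 = 2 are 11C-Glutamine.
- Section 4.1: 1 × 2 = 2 per patient, none of them 11C-Glutamine.
- Over 29 Phase II patients: 29 × 4 = 116 against 29 × 2 = 58. The difference of 58 is all 11C-Glutamine. If accrual stops at 10 patients, the difference is 10 × 2 = 20.

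**3. Patients imaged with 11C-Glutamine**

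- Plan's figure (Table 1): 29. This equals the Phase II maximum.
- Section 4.5 with the calendar: at most 9 in Phase I + 0 in Phase II = at most 9.
- Synopsis version: 29 in Phase II, or up to 29 + 9 = 38 with the sub-study.
- IND expectation: about 15. At most 9 are available within this protocol, so it falls short by at least 15 − 9 = 6.

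The 29 therefore fits the synopsis version and not the cap.

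**4. Patients imaged with 18F-FSPG**

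Table 1 gives 29, the Phase II maximum. Adding the sub-study gives 29 + 9 = 38. Section 4.4 allows patients who are not evaluable for response to be replaced, and the baseline scan precedes treatment (Section 6.2), so replaced patients would add to either number. The table does not say which patients it counts.

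**5. Section 15**

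The plan reuses the 18F-FSPG power and sample size analysis for 11C-Glutamine. It also models RNA-seq expression against both tracers. Research biopsies are taken in Phase II only and 11C-Glutamine scans in Phase I only. As scheduled, no patient supplies both measurements.

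**6. Primary endpoint**

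The two-stage design uses none of these numbers. An exact check of its rule (stop at 0 of 10; claim activity at 4 or more of 29) gives:

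- early stopping under 5%: 0.95^10 = 0.599 (plan: 60%)
- expected size: 10 + 19 × (1 − 0.599) = 17.6 (plan: 18)
- type I error 0.047 and power 0.801

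**The case against.** The strongest reply is that the mismatch is one synopsis line and changes nothing in practice. The synopsis gives only main criteria. It omits consent, age, measurable disease and contraception, so no one could build a working checklist from it alone. Section 4.1 is the list that patients must satisfy in full. The synopsis refers readers to Section 6 for assessments, and Section 6 contains no Phase II visit at which 11C-Glutamine could be given. Much of this stands, and it rules out several stronger readings:

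- **That 58 unplanned 11C-Glutamine administrations are to be expected.** The synopsis line is a willingness criterion and schedules nothing. The 58 measures how far apart the two versions are; it is not a forecast.
- **That eligible patients are being refused.** This cannot be shown, because the checklist is not in the documents. Nor can it be excluded.
- **That a regulatory gate will be missed.** Sections 2.6.2 and 7.12 state an anticipation. Only the Table 1 footnote is firmer, and nothing in trial conduct depends on it. Patients imaged outside this protocol might also contribute.
- **That 11C-Glutamine was once planned for Phase II and then dropped.** No supplied text describes such a change.
- **That the 18F-FSPG count of 29 is wrong and should be 38.** It may cover mandatory Phase II imaging only, and 38 would itself ignore replaced patients.

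The reply does not remove the contradiction. An inclusion criterion that refers to a first-in-human tracer should not depend on staff working out which of two lists governs.

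**Conclusion.** The contradiction is real and stands in the current text: four scans with two tracers in the synopsis, against two 18F-FSPG scans in Section 4.1 and no Phase II 11C-Glutamine in the calendar. Its effect is on eligibility and consent wording. A Phase II candidate who declines 11C-Glutamine passes one list and fails the other.

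Within this protocol at most 9 patients can receive 11C-Glutamine, which fits neither the 29 in Table 1 nor the IND expectation of about 15. That conclusion assumes that the Section 4.5 cap and the calendar hold as written and that no other study contributes patients. The corrections are worth making in the next amendment, but nothing here affects the primary endpoint, its error rates or the stopping rule.

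**What to change.** In the next amendment:

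1. Reconcile the synopsis Dose Expansion criterion with Section 4.1 item 7 and the calendar, so that one requirement appears throughout. Then check the eligibility checklist and consent form against it.
2. In Table 1, correct the 11C-Glutamine count to the sub-study cap of 9. State whether the 18F-FSPG count of 29 covers Phase II only or also sub-study and replaced patients.
3. In Sections 2.6.2 and 7.12 and the Table 1 footnote, restate the 15-patient IND expectation as a number this protocol can reach, or say that patients from outside it will contribute.
4. In Section 15, reconcile the 11C-Glutamine power statement and the RNA-seq model against 11C-Glutamine with the schedule, since biopsies and 11C-Glutamine scans fall in different phases.

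The cost is text editing and a check of two study documents. No procedure is added, and the sample size and primary analysis do not change. The Section 15 edit may mean dropping an 11C-Glutamine analysis that cannot be carried out as scheduled.
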